10 PATIENT ASSESSMENTS

A clinical research nurse will contact each patient by telephone within 2 weeks after the SRS procedure to inquire as to the patient's health status if the patient does not have an appointment with an oncologist at DUMC within that time.

At follow-up visits patients will be evaluated as described in the Table below. Patients will be seen in clinic and undergo repeat MRI imaging as standard of care every 3 months for the first 12 months following completion of SRS and every 6 months for the following 12 months. During the follow up visits, the patient will be examined for new or recurrent neurologic signs/symptoms. On MRI, local recurrence is defined as the reappearance of a metastasis in the SRS treated field (within the 50% isodose line). Each treated lesion will be documented separately. Distant recurrence is defined as the appearance of a new brain metastasis outside the SRS field (completely outside the 50% isodose line). To be deemed a recurrence or new lesion, the lesion must measure at least 5 mm in the axial plane on MRI.

Patients with a recurrent or new lesion, who are symptomatic, may undergo a biopsy to determine if the lesion is secondary to radionecrosis or metastasis. Appropriate salvage therapy will be performed at the discretion of the treating radiation oncologist.

If on evaluation the treating physician decides not to pursue an MRI because of clinical decline, this will not be a protocol violation. The most current brain MRI will be used in the determination of local control. Conversely, if a brain MRI needs to be done at an earlier time point due to medical necessity, an MRI at that time point will also not be a protocol deviation and can be included in the data collection. Brain MRI's may be done at 3 month intervals with a one month before or after allowance.

In addition, included in the category of updated medical history is pertinent interim oncologic and medication history. A medical oncologist overseeing patient's standard of care will have been responsible for chemotherapy management as well as systemic staging scans. We will record the type and duration of systemic therapies with each visit as well as the latest information on staging scans (stable or regression vs. progression of disease).

Study Calendar

	Pre-study	During SRS	First visit post SRS (\approx 4 wks.)	Follow-up Yr.1: every 3-mos. Yr. 2: every 6-mos. (\pm 2 wks.)
Informed Consent	X			
PE including Neurological exam, updated Med History.	X ¹		X	X
Neurocognitive Assessments	X		X ⁴	X ⁴
Performance Status	X		X	X
FACT-Br	X		X	X
Adverse Event Assessment	X	X	X ³	X ²
MRI	X			X ²
Tumor Measurements	X			X ²

1. No more than 15 days prior to SRS.
2. As clinically indicated
3. Acute toxicity will be collected at this visit which will occur approximately 4 weeks' after the last fraction of SRS. If patients are unable to attend follow up due to clinical decline this would not be considered a protocol deviation.
4. It will not be considered a protocol deviation if a patient declines to complete neurocognitive testing at any follow up visit.

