The primary endpoint will be the proportion of patients who live longer than predicted based on the diagnosis-specific GPA score. The Kaplan-Meier estimator will be used to describe the survival of all patients treated with SIMT SRS. Secondary endpoints will be the rate of recurrence at the treated metastases sites, the rate of new brain metastases at a site different from the SRS-treated metastases sites, the rate of death due to neurological causes, and the prevalence of significant adverse events. Exploratory endpoints include change over time in neurocognition and quality of life, quantification of dosimetric measures, the rate of salvage therapy, the rate of radionecrosis at the SRS treatment sites, and the rate and intensity of steroid-usage post-SRS. Dosimetric endpoints to be collected include: maximum and minimum dose to GTV, and conformity index. These endpoints will be compared to historical data calculated by Sperduto et al. from the literature on radiosurgery alone, radiosurgery plus WBRT or WBRT alone, where appropriate.¹⁶ All patients will be evaluated for neurocognitive function via MMSE, HVL, and Trail-making tests A & B, quality of life via FACT-Br, and for local recurrence via MRI every 3 months over the course of the study. These evaluations will be done at regular follow-up evaluations or when local recurrence is suspected on the basis of symptoms. Distant recurrence is defined as the appearance of new brain metastases at a site different from that of the original metastases. Recurrence will further be defined as a new area of enhancement that measures greater than 5 millimeters in the axial plane on MRI. The length of time to recurrence of the original brain metastases will be calculated from the date of the brain metastases radiosurgery to the date that a recurrence was detected by MRI. Patients with suspected recurrent tumor and/or who are symptomatic may undergo a stereotactic biopsy to evaluate for radionecrosis versus recurrent brain metastases, as is standard of care.

There may or may not be a direct medical benefit to participants. The hope is that but the information gained from this study will help in treating patients with brain metastases in the future.

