5 OBJECTIVES AND ENDPOINTS

	Objective	Endpoint	Analysis
Primary	Assess the impact of using SIMT SRS for the treatment of brain metastases on survival	Proportion of patients who live longer than predicted according to the Graded Prognostic Assessment (GPA) score	See Section 13.4
Key Secondary	Describe the time to local brain recurrence	Proportion of patients that experience local brain recurrence within 1 year of SIMT SRS treatment.	See Section 13.5.1
Other Secondary	Describe the time to distant brain recurrence	Proportion of patients that experience a new brain metastasis at a site different from the original brain metastasis site 1 year after SIMT SRS treatment	See Section 13.5.2
Other Secondary	Describe the time to death due to neurological causes	Proportion of patients who are dead within 1 year of SIMT SRS treatment due to neurologic reasons	See Section 13.5.2
Other Secondary	Describe the prevalence of significant adverse events	Proportion of patients who experience grade 3, 4, or 5 neurologic adverse events attributable to SIMT SRS	See Section 13.5.2
Key Exploratory	Describe changes over time in neurocognition	Mean changes from baseline in subscales of the Trailmaking instruments and the HLVT	See Section 13.6.1
Key Exploratory	Describe changes over time in quality of life	Mean changes from baseline in subscales of the FACT-Brain instrument	See Section 13.6.1
Other Exploratory	Quantify treatment set up and dosimetric data for this treatment technique	Mean length of time to set-up and treat patient, Volume of brain exposed to 12Gy, Mean PTV dose, Total volume of all brain metastases, conformity index, maximum dose	See Section 13.6.2
Other Exploratory	Describe the rate of salvage therapy	The proportion of patients who receive salvage treatment after failing SIMT SRS	See Section 13.6.2
Other Exploratory	Describe prevalence of radionecrosis at the SRS site	Proportion of patients with radionecrosis at the SRS site; the proportion of lesions showing radionecrosis	See Section 13.6.2
Other Exploratory	Describe length and intensity of steroid usage post-SRS	Descriptive statistics	See Section 13.6.2

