To summarize, lesions will be treated in one fraction unless a lesion is greater than 3cm, located in the brainstem, or the V12 of the normal brain exceeds 20 cc.

In the setting of multiple metastases, a lesion(s) may need to be resected because of large size or mass effect that causes serious neurologic deficits. The resulting resection cavity/cavities can be treated along with the other unresected metastases with the SIMT technique. This has not occurred commonly in our practice but surgery does not preclude the use of this technology.

Isodose distributions must be calculated, and the prescription isodose line clearly designated, for each target lesion in the transverse, coronal, and sagittal planes. The isodose distributions on the required three planes for each target lesion will include isodose lines (in % dose) that represent 20% dose increments. Cumulative dose-volume histograms must be calculated for all target lesions, as well as the brainstem, optic chiasm, optic nerves, eyes and normal brain parenchyma.

Each lesion will be consistently labeled according to institutional protocol and separately followed and documented. With every MRI, any changes in each lesion will be recorded. MRI image registration using department radiation planning software (iPlan) will aid in detecting differences in lesion size and number.

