10.7 Early Withdrawal of Subject(s)

10.7.1 Criteria for Early Withdrawal

Subjects may voluntarily withdraw from the study at any time. The PI may also withdraw a subject from the study at any time based on his/her discretion. Reasons for PI-initiated withdrawal may include, but is not limited to the following:

- Protocol deviation
- Administrative issues
- Local or distant recurrence evident on Brain MRI imaging

Patients who demonstrate local or distant progression in the brain after study treatment will be followed for overall survival only but will not have neurocognitive testing performed.

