13.4.1 Variable

Though local control is of primary interest in this study, there is concern about the ability to differentiate between swelling due to radiation and disease progression without conducting a biopsy. The use of a biopsy to determine recurrence is not feasible given the number of brain metastases. Hence we focus on the survival of patients with brain metastases who are treated with SIMT SRS. The goal of the study is to confirm that use of SIMT SRS does not reduce the prognosis of patients.

The population of patients with brain metastases is a heterogeneous population with expected survival ranging between 3 and 25 months. We will use the expected survival defined by the diagnosis-specific GPA (Graded Prognostic Assessment) index to assess the efficacy of SIMT SRS.¹⁶ Specifically, for each patient we will determine whether the patient lives longer than expected based upon the GPA index. If the survival of patients treated with SIMT SRS is truly comparable to the survival of patients treated with currently available treatment regimens, then we would expect that approximately half of the patients would live longer than expected.

Hence, the primary endpoint of the study will be the proportion of patients who live longer than expected according to the diagnosis-specific GPA index.

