13.5.1 Key Secondary Objective

The time until local brain recurrence will be calculated as the time between initiation of SIMT SRS and local recurrence of brain metastases. The time to local brain recurrence will be censored at the time of last follow-up if the patient remains alive without local recurrence, or will be censored at death if the patient dies without local recurrence of brain metastases. A Kaplan-Meier estimator will be used to describe the time until local recurrence. Within the context of Kaplan-Meier curve, an estimate of the proportion of patients without local brain recurrence one year after SIMT SRS treatment will be generated. The time until local brain recurrence will also be described within diagnosis-specific subgroups.

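### Local recurrence, the key secondary event, is defined only as reappearance, and no growth criterion covers a treated lesion that persists

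*Combined protocol and SAP*

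**What the plan says.** Section 5 names the key secondary endpoint: "Proportion of patients that experience local brain recurrence within 1 year of SIMT SRS treatment". Section 13.5.1 gives the analysis: "The time until local brain recurrence will be calculated as the time between initiation of SIMT SRS and local recurrence of brain metastases". Patients without the event are censored at last follow-up or death, and a one-year Kaplan-Meier estimate is produced. That section does not say what a local recurrence is.

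The definition is in section 10: "local recurrence is defined as the reappearance of a metastasis in the SRS treated field (within the 50% isodose line". The same paragraph adds a size floor: "To be deemed a recurrence or new lesion, the lesion must measure at least 5 mm in the axial plane on MRI". The synopsis (3.3), directly after defining distant recurrence, says: "Recurrence will further be defined as a new area of enhancement that measures greater than 5 millimeters in the axial plane on MRI".

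Other sections deal with change in treated lesions but do not link it to the event:

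- 9.3: "With every MRI, any changes in each lesion will be recorded". It also uses image registration to help detect differences in lesion size.
- 10.7.1: "Patients who demonstrate local or distant progression in the brain after study treatment will be followed for overall survival only". Progression is not defined.
- 13.4.1, and in the same terms 3.6: "there is concern about the ability to differentiate between swelling due to radiation and disease progression without conducting a biopsy". This is the reason given for a survival primary endpoint.

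Section 13.4.3 lists local control among the considerations for deciding whether SIMT SRS should continue to be used.

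**The concern.** A metastasis can only reappear if it has gone. Intact lesions of up to 4 cm are eligible, so some may leave a visible residual, although the documents do not say how many. If a residual later enlarges, it has not reappeared. Under the section 10 wording the patient stays in the risk set as recurrence-free and is eventually censored, unless another treated lesion meets the definition.

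Failures missed this way can only lower the recorded local recurrence proportion, which makes the technique look better on an outcome that 13.4.3 brings into the overall judgement. If assessors instead count growth informally, they have no threshold, reference scan or confirmation rule, and two readers of the same MRI series could score the patient differently.

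**Working it through.** The documents give no sample size, power or target for local recurrence, so there is no planned figure to reproduce. The check is of the wording, followed by an illustration of scale.

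**Applying the text to three courses of a treated lesion**

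| Course after SRS | Literal reading of section 10 | Loose reading (any lesion in the field of at least 5 mm) |
|---|---|---|
| Disappears, then returns at 8 mm | Event | Event |
| Stable residual of 20 mm | No event | Meets the floor although nothing has changed |
| Shrinks from 20 mm to 10 mm, then grows to 25 mm | No event | Meets the floor at 10 mm, before any growth |

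The measurements are made-up examples. The floor is an absolute size, not a change from baseline or from the smallest measurement. The literal reading therefore misses the third course, and the loose reading cannot separate the second from the third. No section supplies a percentage or millimetre increase, a reference scan or a confirmation rule.

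**The size rules.** Section 10 requires at least 5 mm and 3.3 requires more than 5 mm. They differ only for a lesion of exactly 5 mm.

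**Illustration of scale**

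Inputs:
- True one-year local failure: 100% − 83% = 17%. The 83% is the one-year control quoted in 4.2, from 26 patients with median follow-up of 3.3 months.
- g: the share of failing *patients* whose only local failure is growth of a persisting lesion. This is an assumption; the documents give no value.
- N = 40 (section 13.8), ignoring censoring.

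Formula: recorded rate = 17% × (1 − g).

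| g | Recorded rate | Patients counted out of 40 |
|---|---|---|
| 0 | 17.0% | 6.8 |
| 0.3 | 17% × 0.7 = 11.9% | 4.8 |
| 0.5 | 17% × 0.5 = 8.5% | 3.4 |
| 0.7 | 17% × 0.3 = 5.1% | 2.0 |

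The factor (1 − g) is right only for a patient-level share. If g were a lesion-level share, a patient with k failing lesions would be missed only when all k fail by growth, with probability g^k under independence. At g = 0.5 and k = 2 that is 0.25, so 75% of such patients would still be counted, not 50%.

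**The case against.** The strongest reply is that nothing in the protocol says growth is not a failure, and that the surrounding text suggests the opposite. The worry in 3.6 and 13.4.1 about telling swelling from progression makes sense only if enlarging treated lesions are candidate failures. Section 10.7.1 uses recurrence and progression for what appears to be the same event. Section 9.3 tracks change in every lesion. This stands: a reader might infer that the investigators decided growth should never count, and the documents do not support that. They do support a definition that leaves growth out and, followed to the letter, does not score it.

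A reader might also infer that 3.3 independently excludes growth. That is not secure. The sentence follows the distant-recurrence definition and may qualify only that. Enhancement beyond a treated lesion's former margin could also be called new.

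Three further points carry weight:

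- Counting growth has its own error, because some of it will be radiation effect, which pushes the rate upward.
- Any fixed increment misses something: with 5 mm, growth from 5 mm to 9 mm would not count.
- Requiring confirmation would recreate the problem. Section 10 allows an MRI to be omitted for clinical decline and leaves salvage to discretion, and expected survival starts at 3 months (13.4.1), so confirmation will sometimes never come.

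These points shape the fix. They do not supply the missing criterion.

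Finally, the endpoint is descriptive, with no test or threshold. That limits the consequence but does not make the estimate interpretable.

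**Conclusion.** The concern holds in this form: the operative definition counts only reappearance at 5 mm or more within the 50% isodose line, 13.5.1 uses it unchanged, and no growth criterion exists for a persisting treated lesion. Taken literally, the recorded one-year local recurrence proportion is biased downward whenever any patient fails only by such growth. Taken loosely, the event cannot be scored reproducibly.

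The direction under the literal reading follows from the wording; the size does not. The 11.9%, 8.5% and 5.1% figures rest on an assumed patient-level share and on a 17% rate from a small study with short follow-up, whose own definition of failure the protocol does not give. They should not be read as estimates of the bias in this trial.

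Nor should a reader infer that the trial's main conclusion is at risk. The primary rule (17 or more of 40 living longer than expected) uses survival alone and is unaffected. The definition should be corrected because this is the key secondary endpoint and local control enters the judgement in 13.4.3.

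**What to change.** In section 10, and in 3.3 where it applies:

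1. Define local recurrence per treated lesion as reappearance, or enlargement over that lesion's smallest post-SRS measurement by one prespecified amount (for example 5 mm in the axial plane), dated at first detection.
2. Use one size rule, either at least 5 mm or more than 5 mm, in both places.
3. State that growth with no later MRI or biopsy, because of death, decline or salvage, counts as an event in the main analysis, and that growth shown to be radionecrosis does not. Say in advance how growth that later recedes without biopsy is classified.
4. Report two sensitivity analyses: confirmed events only, and reappearance only.
5. Use the same definition wherever 10.7.1 refers to progression. Reconcile its survival-only follow-up with the three-monthly MRI in 10.7.2, since this determines whether confirming scans are available.

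The cost is mainly wording, plus an axial measurement of each treated lesion at each MRI. Lesions are already uniquely identified (9.9) and followed separately, with changes recorded (9.3), and radionecrosis is already an exploratory endpoint (section 5). The downside is that some radiation-related swelling may be counted and the reported rate may be less favourable; the confirmed-only analysis shows how far that matters. No treatment rule changes.

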10.5 Follow-up Period

Follow-up period will be two years. The first visit is approximately 4 weeks post SRS, every 3 months in the 1st year post SRS, and then every 6 months in the 2nd year within \pm 2-weeks. Each visit will include an updated medical history and physical exam, neurological exam, performance status, adverse events and toxicity assessment, quality of life, and neurocognitive testing. During the follow up period a standard of care contrasted MRI and/or tumor measurements will be performed as clinically indicated by the treating investigator.

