13.5.2 Other Secondary Objectives

The time until distant brain recurrence will be calculated as the time between initiation of SIMT SRS and distant recurrence of brain metastases. The time to distant brain recurrence will be censored at the time of last follow-up if the patient remains alive without distant recurrence, or will be censored at death if the patient dies without distant recurrence of brain metastases. A Kaplan-Meier estimator will be used to describe the time until distant recurrence. An estimate of the proportion of patients without distance recurrence one year after SIMT SRS treatment will be generated. The time until distant brain recurrence will also be described within diagnosis-specific subgroups.

Time to neurologic death is defined as the time between initiation of SIMT SRS and death due to neurologic causes. If a patient remains alive or dies for reasons unrelated to neurologic disease, the time to neurologic death will be censored at the time of last follow-up or death not due to neurologic causes. Analyses similar to other “time to an event” outcomes will be conducted including the generation of Kaplan-Meier curves.

The proportion of patients who experience grade 3 or worse neurologic toxicity attributable to SIMT SRS will be summarized. In addition, adverse events experienced by protocol subjects will also be summarized in several other forms to satisfy scientific and monitoring needs, as well as various regulatory reporting needs (e.g. DCI SOC, and ClinicalTrials.gov). The frequency of adverse events that are possibly, probably, or definitely related to protocol treatment will be tabulated by the maximum grade for each type of adverse event.

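### Recurrence-free time is censored at last contact or death rather than at the last MRI, so patients unscanned because of decline pull the Kaplan-Meier recurrence estimates down relative to complete imaging

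*Combined protocol and SAP*

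**What the plan says.** - **Imaging schedule.** Section 10 has patients "undergo repeat MRI imaging as standard of care every 3 months for the first 12 months following completion of SRS". The study calendar shows no MRI at the 4-week visit. Its footnote makes the follow-up MRI as clinically indicated, and Section 10.5 agrees: "a standard of care contrasted MRI and/or tumor measurements will be performed as clinically indicated by the treating investigator".
- **Missed scans.** Section 10: "If on evaluation the treating physician decides not to pursue an MRI because of clinical decline, this will not be a protocol violation". The next sentence reads "The most current brain MRI will be used in the determination of local control". It sets no limit on the age of that scan and does not say that it must be post-treatment.
- **What counts as an event.** Section 10 defines local and distant recurrence by what MRI shows, and Section 3.3 dates recurrence of the treated metastases by MRI detection. Decline without imaging is not an event.
- **Censoring.** Section 13.5.1: "The time to local brain recurrence will be censored at the time of last follow-up if the patient remains alive without local recurrence"; a patient who dies without local recurrence is censored at death. Section 13.5.2 has the parallel rule: "The time to distant brain recurrence will be censored at the time of last follow-up if the patient remains alive without distant recurrence", again with censoring at death.
- **Endpoint wording.** Section 5 names the key secondary endpoint as the proportion of patients with local recurrence within one year.

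No section defines last follow-up as last imaging, asks for a count of patients without a post-SRS scan, or plans a sensitivity analysis for missed scans.

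**The concern.** A Kaplan-Meier curve treats everyone in the risk set on an event date as someone who could have had the event that day. Here the events fall on scan dates. A patient alive at month 6 whose scan was waived is in the month-6 denominator but cannot be in the numerator. The waiver is also selective: it applies to patients in decline, and brain failure is one possible cause of decline.

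Local control carries weight in this trial. Section 13.4.1 says that it is the outcome of primary interest, set aside as primary endpoint only because it is hard to verify. Section 13.4.3 lists it among the factors that will decide whether further use of SIMT SRS is reasonable. An error of this kind favours the technique under study.

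**Working it through.** The plan states no expected rate, precision or sample size for recurrence, so there is no figure of its own to reproduce. The calculation below illustrates the size.

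**Inputs**
- Scans at months 3, 6, 9 and 12 (Section 10).
- Net one-year recurrence of 25%: assumption.
- Exponential survival with median 5 or 8 months: assumption. With four or more metastases, the best attainable medians in Appendix A are 9.4 months (lung), 4.7 (melanoma) and 7.3 (renal). Breast and GI patients can score higher, and the effect is smaller for them.
- A share q of the scans due within w months of death is skipped: assumption, with q = 50% or 100% and w = 1 or 2 months.
- Decline unrelated to recurrence: assumption, relaxed below.

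**Formulas**
- Recurrence probability per 3-month interval: p = 1 − 0.75^(1/4) = 0.0694.
- Death rate: d = ln 2 / median, which is 0.1386 per month at 5 months and 0.0866 at 8 months.
- Share of the risk set actually scanned: f = 1 − q(1 − exp(−d·w)). Because w is under 3 months, a patient whose scan is skipped dies before the next one, so f is the same at every scan.
- Plan's one-year estimate: 1 − (1 − p·f)^4. Complete imaging: 1 − (1 − p)^4 = 25%.

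Worked case (median 5, w = 2, q = 100%): exp(−0.2773) = 0.758, p·f = 0.0526, and 1 − 0.9474^4 = 19.4%.

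| Median (months) | w (months) | Plan, half skipped | Plan, all skipped |
|---|---|---|---|
| 5 | 1 | 23.5% | 22.1% |
| 5 | 2 | 22.3% | 19.4% |
| 8 | 1 | 24.1% | 23.1% |
| 8 | 2 | 23.2% | 21.4% |

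The shortfall from 25% is 0.9 to 2.8 points with half skipped and 1.9 to 5.6 points with all skipped. Censoring at the last MRI removes the unscanned patients from the denominator, so f becomes 1 and the estimate returns to 25%. Simulation gives the same values within noise.

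**How much comes from patients with only a baseline scan.** Among those alive at month 3, 1 − f miss the first scan: 8% to 24% with all skipped. If only these patients are removed, the worked case becomes 1 − 0.9306 × 0.9474^3 = 20.9%. That recovers about a quarter of the 5.6-point shortfall. Patients who die before month 3 leave before any scheduled scan and do not matter.

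**If recurrence drives the decline.** A second simulation used 17% recurrence (from the 83% one-year control cited in Section 4.2), median survival of 5.5 months, and half or all of the scans due in the last 3 months of life skipped.

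| Recurrence hazard in last 3 months of life | Complete imaging | Plan (half / all skipped) | Last-MRI censoring (half / all skipped) |
|---|---|---|---|
| Unchanged | 17.3% | 14.8% / 12.2% | 17.4% / 17.5% |
| Tripled | 22.2% | 17.3% / 12.2% | 20.3% / 17.5% |

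In the tripled case, last-MRI censoring recovers only part of the loss.

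**The opposite effect of censoring deaths.** The proportion who actually recur before death within a year is r/(r + d) × (1 − exp(−12(r + d))), with r = −ln 0.75 / 12 = 0.0240.
- Median 5: 0.1474 × 0.8579 = 12.6%.
- Median 8: 0.2167 × 0.7348 = 15.9%.

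Every figure in the first table exceeds these.

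**The case against.** **The plan overstates the Section 5 endpoint.** Section 5 names the proportion of patients who experience recurrence. In these scenarios that proportion is about 13% to 16%, while the planned estimate is 19% to 24%. Last-MRI censoring alone moves further from it. This stands. It limits the claim to the planned estimator, and the remedy has to include a competing-risk estimate.

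**Symptomatic patients have a route to imaging.** Section 3.3 provides for evaluation when recurrence is suspected on symptoms. Section 10 accepts an earlier MRI done for medical necessity, and Section 10.7.2 continues three-monthly MRI after withdrawal. This may keep the skip rate low, and it is why the half-skipped column is shown. It does not help a patient judged too unwell to scan.

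**The effect is small against the precision.** In simulated trials of 40 patients with scans skipped in the last 1.5 months of life, the standard deviation of the one-year estimate was 10 to 13 points, against a bias of about 3 to 4. No threshold hangs on the result. This is correct and limits the severity. But the bias has a known direction, and it can be removed in the analysis when decline is unrelated to recurrence.

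**The baseline-scan reading.** A reader might infer that the protocol counts a pre-treatment scan as proof of control. Section 10 does not say so; it only fails to exclude it. That case accounts for roughly a quarter of the shortfall, and most of the effect comes from the censoring rule in Section 13.5. The Section 10 sentence also concerns local control only, so for distant recurrence only the censoring argument applies.

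**Last follow-up might mean last imaging.** This is possible for patients still alive. Censoring at death is explicit, so the problem remains for those who die.

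**Conclusion.** The point holds in a limited form. As written, the rules keep unscanned patients at risk on dates when no event could be found. The planned Kaplan-Meier estimates of one-year local and distant recurrence are therefore too low relative to the same estimator with complete imaging. Under the stated assumptions, the shortfall is about 1 to 3 points if half of the scans due in the last 1 to 2 months of life are skipped, and about 2 to 5.6 points if all are. It is larger if recurrence causes the decline. The direction follows from the text. The size does not, because the documents give no skip rate.

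A reader might go further and conclude that one-year recurrence will simply be under-reported. The documents do not support that: deaths are censored, so the planned figure can still exceed the proportion named in Section 5. The two effects are separate and need separate remedies.

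**What to change.** 1. In Sections 13.5.1 and 13.5.2, censor a patient without recurrence at the last post-SRS brain MRI (at time 0 if there is none) when the next scheduled scan was not done.
2. In Section 10, state that an earlier or baseline scan does not establish local control at a missed visit.
3. Report the one-year cumulative incidence of local and of distant recurrence with death as a competing event, to match the proportions in Section 5.
4. Report how many patients had no post-SRS MRI and how many scans were missed because of decline.
5. Add a sensitivity analysis that counts a scan missed for neurologic decline as a recurrence. It is needed because last-MRI censoring corrects only part of the bias if recurrence drives the decline. Label it an upper bound, since the decline may reflect toxicity.

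**Cost.** This changes wording and analysis only; no scan is added and patient care is unaffected. The reason for each missed scan must be recorded. There will be fewer patients at risk late in year 1 and a somewhat wider interval: in simulation with 40 patients the standard deviation rose from 12.5 to 14.9 points at median survival of 5 months, and from 9.7 to 10.8 at 8 months. The Kaplan-Meier recurrence figure will look less favourable.
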